5.9.8. Overall Survival

In order to better describe the NET patients regardless of their therapeutic management, overall survival will be estimated for all patients, firstly from the time of diagnosis (baseline date = date of diagnosis) and secondly for patients included in the first line of treatment (baseline date = date of 1st line treatment was started if available).

In addition, overall survival (baseline date = date of diagnosis) will also be estimated according to:

- Stage at diagnosis (localised /metastatic),
- Receiving at least one targeted therapy during the data-collection period at any time of the study (yes/no),

- A 1st targeted therapy as line 1 or 2 vs a 1st targeted therapy as line 3 or more at any time of the study,
- Patients having undergone at least one surgery at any time of the study (yes/no).

These analyses will also consider the baseline date as the date of starting treatment at inclusion.

In addition, overall survival will be estimated in metasynchronous patients based on:

- Receiving at least one targeted therapy at any time of the study (yes/no),
- A 1st targeted therapy as line 1 or 2 vs a 1st targeted therapy as line 3 or more.

These two analyses will be duplicated using as the baseline date the date of starting treatment at inclusion, firstly, and the date of diagnosis, secondly.

Overall survival will also be estimated based on the main treatment line by differentiating between the main treatments (baseline date is the start date of each line). Therefore, patients may appear as many times as they have changed their main treatment.

Only the lines at inclusion and subsequently will be considered in the calculation, as the information collected for previous lines is not sufficient to be counted. Overall survival will not be shown if the start date of the main treatment is later than the date of the last visit. Patients still alive when they have completed the line will be censored on the start date of the next line or on the date of receiving the most recent news.

These overall survival analyses will be performed using the method described for analysis of overall survival for the main analysis, the baseline date of which is the date when treatment is started (See above). Analyses will be performed for all patients: a Kaplan-Meier estimator of the survival function for left-truncated and right-censored data will be computed using the SAS PROC PHREG procedure on SAS® software.

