Recorded prospectively	- Follow-up data after enrolment in the study: description of the treatments and tumour assessments (2 years) - Safety (see 7. Pharmacovigilance)	- Characteristics of the patient and description of the disease at the time of starting the study treatment - Initiation of the study treatment and reference data at initiation - Follow-up data after enrolment in the study: description of the treatments and tumour assessments (2 years) - Safety (see 7. Pharmacovigilance)

Table 2 – Data recorded retrospectively and/or prospectively

An end of study questionnaire will be completed by the investigating doctor for every patient who leaves the study before 24 months of follow-up is complete (patients lost to follow-up):

The following data will be recorded for each patient:

Table 3 - Patient variables collected

Table 3 - Patient variables collected					
	initiation of	On initiation of the current treatment line		At the follow- up visits	Anticipated end of study
Patient reference data					
Compliance with inclusion and exclusion criteria			Х		
Social and demographic characteristics (sex, age)			Х		
Medical and treatment history					
Initial diagnosis: date of diagnosis, type of tumour (localised, metastatic)	x				
Description of previous treatments: chemotherapy (type, number of cycles, name of treatments), somatostatin analogue, radionuclide therapy, interferon alpha					
Characteristics of the tumour at treatment initiation (metastases and localisation, symptoms)		х			
Clinical parameters					
Comorbidities and history: renal function, diabetes, heart failure, coronary heart disease, history of cerebrovascular accident, hypertension, hypercholesterolaemia, lung disease (asthma, COPD etc.)		х			
ECOG performance status (score, examination date)			Х	Х	
Status of patient (living, lost to follow-up, deceased and cause of death)					х
Study treatments					
Description of the initiation of treatment: which treatment (targeted therapy or other treatment), date of initiation, dose and treatment regimen, monotherapy/combined treatment		х			
Changes to current treatment: dose changes, temporary interruption, discontinuation and reason for discontinuation			X*	x	x
New treatment line(s) since last visit: which treatment (targeted therapy or other treatment), date of initiation, dose and treatment regimen, monotherapy/combined treatment, dose changes, temporary interruptions, discontinuation and reasons for discontinuation				x	х
Tumour assessment					

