3.4 Safety – onset of adverse events
Has the patient experienced adverse events since the last documented visit on [date of last tumour assessment]
visit entered]? ☐ Yes ☐ No
If yes, please describe all adverse events experienced in the Safety section of the eCRF (see 5. Adverse events recording module)
4. Anticipated end of study form
STATUS OF PATIENT
☐ Alive date of last contact: ☐ / ☐ / ☐ (DD/MM/YYYY) Main reason for stopping the study
Does not meet the inclusion criteria at enrolment - exclusion
□ Patient's decision
☐ Transferred to another treatment centre not participating in the study
Other reason, please state:
□ Lost to follow-up date of last contact: □□/□□/(DD/MM/YYYY)
□ Deceased*
◆ If deceased, please state Date of death
Study medication(s) at the time of death
□ Sunitinib
□ Everolimus
☐ Octreotide ☐ Other treatment, please state:
☐ Chemotherapy
☐ Interferon alpha
☐ Somatostatin analogue other than Octreotide
☐ Radionuclide therapy
Cause of death
☐ Disease progression ☐ Adverse event* not related to a study medication
☐ Adverse event* related to a study medication
,
*Places complete the reference tion of the CDF
*Please complete the safety section of the CRF TREATMENT ONGOING WHEN PATIENT LAST SEEN
THEATMENT ONGOING WHEN FAMILY EAST SEEN
If the anticipated end of study form is completed at a time other than a follow-up visit:
Therapeutic management between the last documented tumour assessment visit on [date of the last documented
visit] and up to the anticipated end of study date:
→ Display section 3.3 Therapeutic management since last tumour assessment
→ Display Table 5 and the screens corresponding to each recorded treatment line
DISEASE OUTCOME

Novartis Pharma S.A.S. - Pfizer S.A.S

Page 85 of 90

Observational study protocol $final\ version\ of\ 17/07/2018$

Best response to treatment when patient	last seen	
☐ Complete response	☐ Stable disease	
☐ Partial response	☐ Disease progression	
Date of the last disease assessment: \\ \\ \ \ \ \ \ \ \ \ \ \ \ \ \ \ \ \		

Please complete the adverse events table for all events reported since inclusion in the study: Description of the adverse event: Table 4 - Safety											
Description the event		Date onset	of	Outcome	Severity	CTCAE grade	Seriousn ess	Causality of the study treatment	Action concerning the study treatment		
History of	pre	viously	des	cribed adverse events	s						

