4.7. Derived Variables

• Total duration of exposure to the documented treatment in the study (months)

(Date of last receipt of treatment – Date of first receipt of treatment + 1)/30.4375

For patients who drop out of the study early, the date of last receipt of the treatment considered will be the date of the last visit.

To analyse exposure times by treatment received at least once during the study, if the start date is after the date of the last visit, the treatment will not be considered.

In terms of exposure time for treatments used in combination, the start date and end date of the combination were not recorded in the CRF. The visit prior to the report describing addition of the combination will be deemed to be the start date and the visit in which the combination is reported as being discontinued will be deemed to be the end date for the combination, unless the combination began or finished during a line of treatment (or includes the start and end date).

• In general, the time between two dates expressed in days will be obtained as follows:

Most recent date – Least recent date

The following conversion factors will be used to convert the times into months or years:

- 1 month = 30.4375 days
- 1 year = 365.25 days
- Age (in years) will be calculated as follows:

(Inclusion date – Date of birth)/365.25

• The disease duration (in years) will be calculated as follows:

(Inclusion date – Disease start date)/365.25

• The disease duration (in years) at start of the current treatment at inclusion will be calculated as follows:

(Treatment start date - Diagnosis date) / 365.25

• Time until first temporary discontinuation since inclusion into the study:

(Date of first temporary discontinuation – Date of inclusion + 1)/30.4375

• Time until permanent treatment discontinuation since inclusion into the study:

(Date of final discontinuation – Date of inclusion + 1)/30.4375

• Lines of cancer treatment:

Treatment lines will be defined in two ways:

- Main treatment line: All new treatments will be considered as a new main treatment line.
- Main concomitant treatment line: All new treatments or new combinations will be deemed to be a new concomitant treatment line.

The reason for discontinuing treatment will not be considered in the definition of a treatment line.

The same treatment stopped for over 3 months will be deemed to be two different lines of treatment and to be one line if the discontinuation lasts for less than 3 months.

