Analyses of progression-free survival will also be conducted on patient subgroups by main treatment line and by main treatment. These analyses will be calculated from the start of each line (ie, the baseline date will be the start date of the main treatment of any new line after changing the main treatment). Therefore, patients may appear as many times as they have changed their main treatment. Only the lines at inclusion and subsequently will be considered in these analyses, as the information collected for previous lines is not sufficient for a survival analysis. Progression-free survival according to the main treatment lines will not be shown if the start date of the main treatment is later than the date of the last visit. In addition, for this analysis, patients will be censored based on the date of the last tumour assessment or clinical assessment for the line, when patients change line without reporting a progression. When there is no date for the tumour or clinical assessment, patients will be censored on the date they discontinued treatment in relation to the line being analysed.

Progression-free survival by subgroup will be analysed using the method described for analysing progression-free survival in the main analysis, which uses as the baseline date the date of starting the main treatment at inclusion (see above). The Kaplan-Meier method, with right censoring and left truncation, uses the PROC PHREG SAS® procedure.

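### By-line OS and PFS, and one exposure analysis, exclude treatment lines started after the last visit; deaths on those lines are lost, so survival on post-inclusion lines reads somewhat too high

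*SAP*

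**What the plan says.** The same exclusion appears in three places in the SAP.

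- By-line OS (5.9.8): "Overall survival will not be shown if the start date of the main treatment is later than the date of the last visit".
- By-line PFS (5.9.7): the estimate "will not be shown if the start date of the main treatment is later than the date of the last visit".
- Exposure by treatment received at least once during the study (4.7): "if the start date is after the date of the last visit, the treatment will not be considered".

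For by-line OS, section 5.9.8 also says: "Patients still alive when they have completed the line will be censored on the start date of the next line". The alternative censoring date that it allows is last news, which is thus a different date from the last visit. Section 5.9.7 has a fallback for a line with no assessment date, which is censoring at discontinuation of that line.

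The protocol collects what is needed for the excluded lines. Table 3 (section 5.2.2) lists, at the anticipated end of study, "Status of patient (living, lost to follow-up, deceased and cause of death". Section 4 of the case report form covers the gap after the last visit: "If the anticipated end of study form is completed at a time other than a follow-up visit", it reopens the treatment section and Table 5 under the title "Therapeutic management between the last documented tumour assessment visit on" (the date of that visit follows), up to the end-of-study date. It also records the date of death or of last contact.

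The SAP expects such lines. Footnotes to the care-pathway position tables (9.3.2.1) list patients whose last main line starts after the last visit. The survival and exposure templates have no such footnote, no count or sensitivity analysis is planned, and section 6 does not list the rule as a limitation.

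**The concern.** Keeping a line depends on something that happens after the line's own time zero. A line started between two visits stays in the analysis only if the patient attends a later visit. Among retained lines, the time from line start to the next visit is free of deaths by construction. If the patient dies first, the line and the death are both removed.

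The previous line does not recover the death, because it was censored when the new line began. The left-truncation method in 5.5.1 corrects for entry at inclusion and does nothing about this later selection.

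At stake is the description of survival on second and later lines, which is what readers will look at for treatments used late in the disease. In the exposure analysis, the rule removes very short exposures, so mean exposure reads too long.

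**Working it through.** **Inputs from the documents.** Visits are about 2 to 3 months apart and not imposed (SAP 3.3). A line started on the last visit date is kept, because only later dates are excluded. The only OS median given is 38 months, for pNET in general, from a cited study (protocol section 2).

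**Assumptions.** The documents give neither survival on later lines nor the delay from a visit to the start of a new line. I assume exponential survival from line start with median m = 12, 24 or 38 months, and a time d from line start to the next visit.

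**The plan's own figure.** There is none for excluded lines. For scale, the planned precision reproduces: 1.96 × √(0.25/150) = 0.080 and 1.96 × √(0.25/75) = 0.113.

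**Formulas.** With S(t) = 2^(−t/m):
- fraction of lines dropped = 1 − E[S(d)]
- 12-month OS among retained lines = S(12) / E[S(d)]

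where E averages over lines and d = 0 for a line started on a visit day.

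**Worked cases.**
- m = 12, every line exactly 2 months before the next visit: S(2) = 2^(−2/12) = 0.891, so 10.9% of lines are dropped, all of them deaths. OS at 12 months reads 0.500/0.891 = 56.1%, and the median shifts by d, from 12 to 14 months.
- m = 12, half of lines on a visit day, the rest with d uniform from 0.25 to 2.25 months: the average of S(d) over that uniform range is 0.931, so overall E[S(d)] = 0.5 + 0.5 × 0.931 = 0.965. OS at 12 months reads 0.500/0.965 = 51.8%.

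| Timing of line starts | m = 12 (true 50.0%) | m = 24 (true 70.7%) | m = 38 (true 80.3%) |
|---|---|---|---|
| Half on visit day, rest d uniform 0.25–2.25 | 51.8% | 72.0% | 81.3% |
| Half on visit day, rest d uniform 2–2.75 | 53.4% | 73.1% | 82.1% |
| All between visits, d uniform 0–2 | 52.9% | 72.8% | 81.8% |
| All exactly 2 months before a visit | 56.1% | 74.9% | 83.3% |
| All between visits, d uniform 2–2.75 | 57.3% | 75.7% | 83.9% |

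**Does dropping lost or administratively ended patients cancel this?** No. A simulation of 300,000 lines in each of 54 scenarios (three medians, visits 2 or 3 months apart, three start patterns, loss of 0, 10 or 30% a year, end at 24 months) gave an upward shift in every one, of about 1 to 7 points at 12 months. The rule removed about 1–18% of post-inclusion lines and 8–34% of the deaths on them.

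**Dilution.** By-line curves pool inclusion lines with later ones, and the rule hardly touches inclusion lines. If half the entries were inclusion lines (an assumption), the first case above becomes 0.500/(0.75 + 0.25 × 0.931) = 50.9%, an excess of 0.9 points instead of 1.8.

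**Exposure.** For drop-outs, 4.7 takes the last visit as the last dose. A line started 20 days after it (an illustration) would have exposure (0 − 20 + 1)/30.4375 = −0.6 months. The exclusion in 4.7 avoids that impossible value, so it cannot be deleted on its own.

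**The case against.** The strongest reply is that the SAP never defines the last visit. Protocol 5.2.2 lists the end-of-study contact among the visits, and 9.1.2 pairs a last visit with the end-of-study questionnaire. If that form counts as a visit, a line started before a death recorded on it might be kept and the loss would shrink. This stands as a real ambiguity. Against it, the form provides for completion outside a follow-up visit, and 5.9.8 separates last visit from last news. The reading used here is the better supported one, but it is not certain.

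The size is also open to challenge. The case report form expects lines put in place at the visit itself, and those are kept. A reader might take 56.1% against 50.0% as the expected bias; nothing in the documents supports every line starting 2 months before a visit. Line-by-treatment groups will also be small, so sampling error will usually exceed a shift of 1 or 2 points.

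A reader might further infer that these patients vanish from the study, or that the primary results are inflated. Neither follows. Main OS runs from the start of the inclusion treatment and still counts the death, primary PFS concerns the inclusion line only, and the deaths and the lines are listed (SAP 5.7.3, Listing 16.2.5). Nor does distortion of treatment comparisons carry much weight, since the documents already call strict comparisons inappropriate.

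The rule may be meant to drop lines with no follow-up. For patients alive or lost with no later assessment, dropping the line costs PFS essentially nothing. The harm comes from also dropping observed deaths, and any progression recorded on the end-of-study form.

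**Conclusion.** The point holds for the additional by-line OS and PFS analyses and for one exposure analysis, provided the last visit means the last tumour assessment visit. On that reading, the upward direction for by-line survival follows from the rule itself and was the same in every scenario examined.

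The size cannot be derived from the documents. Under exponential survival with medians of 12 to 38 months, it is about 1 to 2 points at 12 months when half of lines start on visit days (3.4 in the least favourable such case), and up to about 6 to 7 points if all start between visits. It is smaller where inclusion lines are pooled in. All figures are for OS; none was calculated for PFS or exposure. Primary analyses are not affected, so this should be corrected but does not threaten the main result.

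**What to change.** - **SAP 5.9.7 and 5.9.8:** delete the exclusion and include every line at or after inclusion with a recorded start date.
- **By-line OS:** follow each line to death or last news.
- **By-line PFS:** count death or a recorded progression on the line as an event. With no assessment on the line, censor at line start, and amend the discontinuation-date fallback in 5.9.7 to match.
- **SAP 4.7 and the exposure footnotes (Tables 14.3.1.x):** for lines started after the last visit, end exposure at the recorded stop date, death or last contact. Then drop the exclusion; doing so first would create negative exposures.
- **Definition and reporting:** define the last visit, stating whether the end-of-study form counts, and report the number of affected lines with their outcomes.

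If the rule is kept, run the all-lines analysis as a sensitivity analysis and add the limitation to section 6.

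The cost is a few SAP and footnote edits and minor programming; the data fields already exist. By-line survival becomes slightly less favourable.

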5.5. Analysis of the Primary Objective

The following parameters will be analysed in the reference set in order to meet the primary objective of the study:

• Progression-free survival at 2 years when receiving the main treatment at the time of inclusion. Progression-free survival is defined by the time between starting treatment (the sequence ongoing at the time of patient inclusion into the study) and the date of

first documented disease progression or all-cause death when receiving the main treatment at the time of inclusion.

- Overall survival rate at 2 years. Overall survival is defined by the time between starting treatment (the sequence ongoing at the time of patient inclusion into the study) and all-cause death.
- Treatment safety (targeted therapies and other treatments) during the prospective period of the study described in terms of treatment discontinuations and the reasons for these, adverse events (graded according to CTCAE version 4.0, May 2009) and any complications of these adverse events. This analysis is described in Section 5.7.

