5.5.1. Analysis of Progression-free Survival and Overall Survival

Progression-free survival and overall survival will be measured using the Kaplan-Meier method. The survival function S(t) will be the likelihood of event of interest (progression or death respectively) not occurring before the date t. This function will be represented graphically with a survival curve.

These analyses will be carried out as shown in the table below:

	Progression-free survival	Overall survival
Start date	Date of starting (the treatment patient inclusion) of the target	
Date of event	Date of progression or death when receiving the main treatment at the time of inclusion	
Right censoring	Patients without an event when receiving the main treatment at the time of inclusion or lost to follow-up will be censored at the last recorded time to progression or the last tumour assessment, last disease assessment in the early study completion form, when receiving the main treatment at the time of inclusion. For patients without a tumour assessment but with a clinical assessment, the date of the tumour assessment visit will be used in the PFS analysis. If patients have both a	Patients with no event or lost to follow-up or alive at the end of the study will be censored at their last follow-up date (last follow-up date or last news).

Progression-free survival	Overall survival
tumour and clinical	
assessment, the maximum	
time between the date of the	
visit and the assessment date	
will be used in patients with	
no disease progression.	
When there is no tumour or	
clinical assessment date,	
patients will be censored	
using the treatment	
discontinuation date.	

Progression: information obtained from the "tumour assessment" section, tumour assessment visit or the "disease progression" section in the early study completion form or in the "treatment discontinuation" section if the main treatment is discontinued for disease progression.

Death: information obtained from the "patient status" section in the early study completion form or in the "outcome" section of the adverse event record page.

In the progression-free survival analysis, the first progression when receiving the main treatment at the time of inclusion will be used, either radiological progression or clinical progression if this occurs first.

The following details will be presented in summary tables:

- Number of patients;
- Number of events (with details of progression/death);

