- Number of right censors (with details of patients who are lost to follow-up, no disease progression/death);
- Survival (in months): median (+95% CI), Q1 (+95% CI), Q3 (+95% CI), minimum, maximum;
- Estimated survival rate at a specific time (for example 6 months, 1 year and 2 years): number of subjects at risk, survival rate at each time.

These survival rates will be estimated and described in each of the following groups and subgroups:

- Targeted therapies group (with an estimate in the Everolimus and Sunitinib subgroups);
- Other treatments group (with an estimate in the chemotherapy, somatostatin analogs, interferon alpha and metabolic radiotherapy subgroups).

Handling of truncation/left censoring:

The study includes a retrospective and/or prospective data collection period depending on whether the patient is prevalent or incident in terms of his/her tumour treatment at the time of inclusion into the study.

The time to event of interest ("survival" time) or censoring if no event occurs (right censoring) will be based on the treatment line start date at the time the patient was included into the study.

As a result, when patients are recruited into the study, those patients who have already died on treatment could not be included, whereas patients who were still alive on treatment were included. This is left truncation.

In addition, the prevalent patients included could progress before inclusion into the study and not stop the treatment started or ongoing at the time of inclusion. This progression could not be identified and is a left censoring.

In practice, after disease progression on a given treatment, the treatment is changed. As a result, prevalent patients we observed on a given treatment at inclusion could not by definition experience disease progression.

As a result, we also do not see patients on a given treatment at inclusion who progressed on the same treatment prior to entering the study and we therefore deem these cases to be left truncations.

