6.1.3. Left Truncation and Left Censoring

Left truncation bias is present for prevalent patients who started ongoing treatment prior to inclusion into the study because of the impossibility of including patients who have died into the study. The prevalent patients also exhibit left censoring bias because of the lack of retrospective collection of tumour assessment data.

These sources of bias are taken into account in the overall survival analysis and progression-free survival analysis using the statistical method described in Section 5.5.1.

Incident patients contribute to the survival curve from their baseline date. Conversely, prevalent patients are only at risk of developing an event from their inclusion into the study onwards and therefore do not contribute to the survival curve from their baseline date, although do contribute from a later date after their inclusion into the study. All patients from the reference set will therefore be taken into account into the survival analysis although patients whose treatment started two years before the beginning of the study will only be included after a two-year follow-up period and will therefore not be included in the estimation of the two-year survival rate. This is a limitation of the study.

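### Additional survival analyses (SAP 5.9.7–5.9.8): by-line "OS" stops at the next treatment line, and curves are grouped by treatment that may start after inclusion, so curves can differ with no treatment effect

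*SAP*

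**What the plan says.** SAP 5.5 sets the primary endpoint: "Overall survival is defined by the time between starting treatment" and all-cause death. The table in 5.5.1 adds that patients without an event, lost to follow-up or "alive at the end of the study will be censored at their last follow-up date". Groups in the primary analysis are defined by treatment at inclusion.

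SAP 5.9.8 then adds three things:

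- **OS by main treatment line.** Time zero is the start of each line, and a patient appears once per line. Patients alive at the end of the line "will be censored on the start date of the next line or on the date of receiving the most recent news". The section also says the main-analysis OS method will be used, although the main analysis has no such censoring rule.
- **OS split by targeted therapy (TT):** "Receiving at least one targeted therapy during the data-collection period at any time of the study (yes/no"), and "A 1st targeted therapy as line 1 or 2 vs a 1st targeted therapy as line 3 or more". Both splits are repeated in metasynchronous patients.
- **OS split by surgery at any time of the study.**

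That makes five OS splits, with diagnosis and the start of the inclusion treatment as time origins.

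SAP 5.9.7 applies similar groupings to PFS on the inclusion treatment, in eight splits:

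- any TT at any time: all patients, first-line patients, second-line patients (three splits);
- two or more TTs versus one at any time;
- line of first TT: all patients, metasynchronous patients (two splits);
- surgery at any time;
- total number of lines over the whole follow-up, in patients on chemotherapy at inclusion.

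On what drives a change of line, 5.5.1 says: "In practice, after disease progression on a given treatment, the treatment is changed".

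**The concern.** There are three separate faults.

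1. **Informative censoring.** If a new line usually follows progression, censoring at the next line removes patients when their prognosis changes, and their later deaths never count. The curve describes survival while on the line, under the title of overall survival.
2. **Grouping OS on the future.** A patient must survive to receive a later TT or operation. The time survived until then is credited to the exposed group. Delayed entry does not cure this: it reflects that "prevalent patients are only at risk of developing an event from their inclusion into the study onwards", so it removes only time before inclusion.
3. **Grouping PFS on its own outcome.** If later lines follow progression, having a later TT, a second TT or more lines partly means having progressed early on the inclusion treatment.

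According to the protocol's justification section, the health authority asked about impact relative to other treatments. Ever/never TT curves invite that reading. SAP 6.4 warns only of confounding by choice of treatment and offers Cox adjustment for patient characteristics, which does not repair grouping on later events.

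**Working it through.** **The plan's own precision.** From SAP 4.2, the half-width is 1.96 × √(0.25/n). For n = 150 this gives 0.080 and for n = 75 it gives 0.113, both as stated. For a difference between two groups of 75: 1.96 × √(2 × 0.25/75) = 0.160.

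**Inputs.** The 38-month median OS comes from the protocol (section 2, Prognosis). All other rates are assumptions, because the documents give no switching rates, times to progression or times to later TT. All patients are identical and treatment has no effect.

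**1. By-line OS.** Assume a median PFS of 12 months, a death hazard of 0.004 per month on the line and 0.03 after progression, with every progressor switching at once.
- Exit hazard from the line: a = ln 2/12 = 0.05776. Progression hazard: p = 0.05776 − 0.004 = 0.05376. Let b = 0.03.
- True S(24) = e^(−24a) + p[e^(−24b) − e^(−24a)]/(a − b) = 0.250 + 0.05376 × (0.4868 − 0.250)/0.02776 = 0.709.
- The SAP rule keeps only on-line deaths: e^(−24 × 0.004) = 0.908. The error is +20 points.
- With median PFS 18 and hazards 0.008 and 0.02, the same formulas give 0.763 against 0.825, or +6 points.

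Simulation (300,000 patients per scenario) extends this. Non-switchers have a death hazard of 0.10–0.20 in the partial-switching rows.

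| Who switches | By-line OS minus true OS at 24 months |
|---|---|
| All progressors; mortality rises 2.5–7.5 fold | +6 to +20 points |
| 85% of progressors | +3 to +11 |
| 30–70% of progressors | −4 to +7 |
| Only the fitter 30–70%; post-progression mortality 1–1.5 times on-line | −25 to −2 |

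If mortality is constant and switching is unrelated to prognosis, the error vanishes (0.645 against 0.645).

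**2. OS by ever/never TT.** Take constant mortality λ = ln 2/38 = 0.01824, so true S(24) = 0.645. Half the patients are on TT at inclusion. The others start TT at rate μ = ln 2/12 = 0.05776 (assumed).
- Others alive and untreated at 24 months: e^(−24(λ+μ)) = 0.161.
- Others who die first: λ/(λ+μ) × (1 − 0.161) = 0.24 × 0.839 = 0.201.
- Never-TT survival: 0.161/(0.161 + 0.201) = 0.445.
- Ever-TT survival: (0.645 − 0.5 × 0.161)/(1 − 0.5 × 0.363) = 0.690.

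The gap of about 25 points comes entirely from the grouping. Simulation gave 0.691 against 0.440. With half the patients prevalent and delayed entry applied, it gave 0.701 against 0.411.

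A second model makes later TT follow progression. The 24-month gap, ever minus never, is then:
- +6 to +20 points if progression does not change mortality (+6 to +22 with delayed entry);
- −7 to +9 if it raises mortality 2–7.5 fold;
- +1 to +20 if 15–30% of progressors are too unfit to switch.

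For line of first TT, line 3 or later minus line 1–2 is −1 to +6 points. Grouping by exposure known at inclusion leaves a gap within 0.4 points.

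**3. PFS on the inclusion treatment.** With median PFS 9 months, 12-month PFS is 2^(−12/9) = 0.397. Among patients with an event by 24 months it is (0.397 − 0.157)/(1 − 0.157) = 0.284. Selecting on a later consequence of progression therefore lowers PFS by itself. In simulation with hazards 0.008 and 0.03, and each later line being TT with probability 0.5:

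| 12-month PFS | Values | Range over scenarios |
|---|---|---|
| Ever vs never TT | 0.350 vs 0.536 | 2–29 points lower |
| Two or more vs one TT | 0.220 vs 0.393 | 9–28 lower |
| More than 2 vs 2 or fewer lines | 0.311 vs 0.581 | 7–30 lower |

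The low ends come from 70–85% switching. The total-lines row used mixed lines at inclusion, not the SAP's chemotherapy subgroup alone. Grouping by TT or line at inclusion leaves a gap within 0.5 points.

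**The case against.** These are additional, descriptive analyses. The SAP plans no test on them and says elsewhere that treatment comparison is not strictly appropriate. That stands, and it limits the seriousness. It does not make the curves right: the caveat concerns confounding, and a descriptive curve labelled OS should still estimate OS.

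The sizes are weakly anchored, and the large ones need different premises. The +20 for by-line OS needs progression to raise mortality, whereas the ever/never OS gap then straddles zero. The 38 months refers to pNET patients generally. Diagnosis as time origin was not simulated. Some ranges (−7 to +9, −1 to +6) lie inside the 16-point half-width for two groups of 75. All of this stands, so the figures are not predictions for this study.

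The PFS result leans on progression triggering the next line. The CRF also lists adverse events, scheduled stops and patient or doctor decisions as reasons for stopping, and SAP 4.7 lets a long pause or a combination define a new line. More such switching weakens the effect. Surgery was not simulated, and the progression argument does not carry over to it; only the survive-until-exposed argument does.

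Censoring at the next line does avoid counting one death in several line curves. That is a real trade-off, but it calls for a different label.

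**Conclusion.** The concern holds for the additional analyses only. By-line "OS" departs from the SAP's own definition of OS. The five OS splits and eight PFS splits group patients on facts that may arise after time zero, and neither left truncation nor covariate adjustment corrects this. Followed as written, these tables can show differences where treatment has no effect.

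The direction is unknown for by-line OS and for the OS splits. For PFS, every scenario run showed lower values with later TT, a second TT or more lines, given that later lines follow progression. The existence of the artefact rests on the SAP's rules and its statement about treatment change; the sizes rest on assumed rates. It should be fixed before the tables are produced, but it does not threaten the primary results.

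**What to change.** - **By-line OS:** follow each patient to death or last news, as in 5.5.1, and state that one death then counts in every line curve in which the patient appears. Alternatively, keep the rule and title the tables survival while on the line.
- **OS splits:** group only by exposure known at inclusion: prior TT, treatment and line at inclusion, prior surgery.
- **If later TT is still to be shown:** use time-dependent entry and exit from the line start dates already collected in the CRF, as description only. State that this removes the survival-until-exposure time but not confounding by progression. In the null simulations the death rate ratio was 0.98–1.01 with constant mortality, but 1.12–2.71 when progression raised mortality and 1.02–1.51 when 15–30% of progressors could not switch. Do not assume a start date exists for surgery recorded as a combination; SAP 4.7 says combination dates were not collected.
- **PFS on the inclusion treatment:** group only by facts known at the start of that line or at inclusion, and drop the at-any-time and total-lines splits.

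The cost is SAP wording, modest reprogramming and fewer or smaller subgroup tables. Grouping at inclusion needs no new data.
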